#### 9.2.1.2 Pharmacist Selection

Pharmacists will be recruited via IQVIA's trusted and assessed vendor M3 Global Research (https://www.m3globalresearch.com/) (34-36). M3 Global Research may work with partner panels where appropriate; in such instances, clients are aware and multiple safeguards are employed to ensure data integrity. This includes on-the-spot deduplication using digital fingerprinting technology, as well as sharing of exclusion lists.

For this study, M3 Global Research will be using their proprietary panel in Germany, Spain, Italy, Belgium and Sweden and then working with partners in Greece and Poland.

M3 Global Research adapts its recruitment methodology based on geographies and target groups. For some target groups, a pure online recruitment approach may not suffice or may not be appropriate, such as for hard-to-reach participant targets. In such instances, other recruitment approaches - such as phone-to-web - may be more appropriate. M3 Global Research transparently advises its clients on the recruitment methodologies planned for each project. M3 Global Research has in-house capabilities for telephone recruitment across its locations spanning over 10 markets. In addition, M3 Global Research works with trusted local partners, educates them on all relevant quality standards, and works with these partners to reach hard-to-reach audiences.

- For France, Germany, and Sweden, M3 Global Research will use their International Organisation for Standardisation (ISO) certified panel for recruitment to this online survey and would expect a mix of settings/locations based on natural fall out from our panellists.
- For Poland, M3 Global Research would be using an external preferred supplier who
  has signed an agreement with them to ensure that they comply with M3 Global
  Research's ISO standards. For recruitment, M3 Global Research's local team would

Template No.: RWI\_TP\_EPI0016 Revision 1 Reference: RWI\_WI\_EPI0005

Protocol/Study No: SC02 EMA/2018/19/PE

Page 29 of 92

be pre-recruiting pharmacists to then complete the online survey and would expect a mix of settings/locations based on natural fall out from our panellists.

• For Greece, M3 Global Research would also be using an external preferred supplier who has signed an agreement with them to ensure that they comply with M3 Global Research's ISO standards. For recruitment, M3 Global Research's local team would be using online recruitment and would expect a mix of settings/locations based on natural fall out from our panellists.

M3 Global Research follows an extensive partner vetting process, which meets ISO 26362 International Standard requirements. All partners are carefully selected and presented the standard as well, to ensure all recruiting parties provide the best possible service to the clients. Partners are reviewed by project staff on each project as well as regularly audited by M3 GR's dedicated team. M3 Global Research provides notification to clients in advance when using third party providers.

#### 9.2.1.3 Patient Selection

Patients will be recruited via M3 Global Research and GLocalMind (http://www.glocalmind.com) vendor panel. As an alternative strategy, patients could have been recruited via prescribers, but this approach would have led to a much more elevated fee. We therefore opted for a direct-to-patient approach.

# Patient selection by M3 Global Research:

Details on M3 Global Research and their general recruitment methodologies are provided in Section 9.2.1.2.

- For France and Germany, M3 Global research would still use their internal panel of respondents but will also need to supplement their panel with trusted partners.
- For Poland, M3 Global research would be using an external preferred supplier and they would be pre-recruiting patients to then complete the online survey.
- For Greece, M3 Global research would also be using an external preferred supplier and they would be using online recruitment.

M3 Global Research uses a mixed approach for patient recruitment made up primarily of online panel recruitment and then also including social media campaigns, telephone recruitment and can also offer HCP referrals for certain projects. They do not use river sample for recruitment as respondents will not always be on a panel/be verified and they always aim to provide verified respondents.

# Patient selection by GLocalMind:

GLocalMind may work with partner panels where appropriate; in such instances, clients are aware and multiple safeguards are employed to ensure data integrity. This includes onthe-spot deduplication using digital fingerprinting technology, as well as sharing of exclusion lists.

Template No.: RWI\_TP\_EPI0016 Revision 1 Reference: RWI\_WI\_EPI0005

Protocol/Study No: SC02 EMA/2018/19/PE

Page 30 of 92

GLocalMind adapts its recruitment methodology based on geographies and target groups. For some target groups, a pure online recruitment approach may not suffice or may not be appropriate, such as for hard-to-reach participant targets. In such instances, other recruitment approaches, such as phone-to-web - may be more appropriate. GLocalMind transparently advises its clients on the recruitment methodologies planned for each project. GLocalMind has in-house capabilities for telephone recruitment across its locations spanning over 10 markets. In addition, GLocalMind works with trusted local partners, educates them on all relevant quality standards, and works with these partners to reach hard-to-reach audiences.

- For Sweden, GLocalMind will use their International Organisation for Standardisation (ISO) certified panel for recruitment to this online survey and would expect a mix of settings/locations based on natural fall out from our panellists.
- For Poland, GLocalMind would be using an external preferred supplier who has signed an agreement with them to ensure that they comply with GLocalMind's ISO standards. For recruitment, GLocalMind's local team would be pre-recruiting pharmacists to then complete the online survey and would expect a mix of settings/locations based on natural fall out from our panellists.

GLocalMind follows an extensive partner vetting process, which meets ISO 26362 International Standard requirements. All partners are carefully selected and presented the standard as well, to ensure all recruiting parties provide the best possible service to the clients. Partners are reviewed by project staff on each project as well as regularly audited by GLocalMind GR's dedicated team. GLocalMind provides notification to clients in advance when using third party providers.

In order to reduce the eventual risk of unavailability of M3 Global Research and/or GLocalMind, IQVIA will line up another vendor to replace M3 Global Research in the time of field work, if required.

#### 9.2.2 Inclusion Criteria

The following criteria must be met in order to be enrolled in the study:

- For prescriber questionnaire: Prescribers who have prescribed MTX in a single low dose once a week for indications that require weekly dosing in the past 3 months
- For pharmacist questionnaire: Pharmacists who have dispensed MTX in a single low dose once a week for indications that require weekly dosing in the past 3 months
- For patient questionnaire: Patients who have been treated with a single low dose once a week for indications that require weekly dosing in the past 3 months

Template No.: RWI\_TP\_EPI0016 Revision 1 Reference: RWI\_WI\_EPI0005

Protocol/Study No: SC02 EMA/2018/19/PE

Page 31 of 92

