#### **Population:**

The following criteria will be checked at the beginning of the web questionnaire:

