# 8. RESEARCH QUESTION AND OBJECTIVES

The aim of the current study is to examine the effectiveness of product-specific risk-minimisation measures for MTX, by carrying out a survey to evaluate the impact of European union (EU) label changes for medicinal products containing MTX for weekly administration, with reference to the 2019 referral procedure (refer Section 7.2).

The primary objectives of the study are:

Template No.: RWI\_TP\_EPI0016 Revision 1 Reference: RWI\_WI\_EPI0005

Protocol/Study No: SC02 EMA/2018/19/PE

Page 24 of 92

- To determine the extent of prescriber awareness and knowledge of the risk of inadvertent overdose due to daily instead of weekly use and adherence to SmPC recommendations for oral and parenteral MTX-containing medicines with at least one indication requiring once-weekly dosing, with particular focus on the following elements:
  - 1.1. Receipt and awareness of the DHPC
  - 1.2. Knowledge of the dosing frequency of MTX in the treatment of inflammatory diseases (e.g. rheumatologic/dermatological diseases or Crohn's disease), by indication
  - 1.3. Knowledge of the updated posology instructions and boxed warning
  - 1.4. Receipt and awareness of the new or updated EMs for HCPs (checklist or guide) and awareness of the patient card to avoid the risk of inadvertent overdose due to daily instead of weekly use
- 2. To determine the extent of pharmacist awareness and knowledge of the patient card, the visual reminder on the outer packaging and the need to mark the day of intake for indications requiring once-weekly dosing regimens, and adherence to marking the day of intake on the outer packaging
- 3. To determine the extent of patient awareness and knowledge of the following elements introduced to avoid incorrect administration schedules for oral and parenteral MTX-containing medicines with at least one indication requiring once-weekly dosing:
  - 3.1. Receipt and awareness of the patient card, and knowledge of symptoms of MTX overdose and the purpose of the patient card (i.e. to note the day of intake for indications requiring once-weekly dosing regimens, and steps to be taken if symptoms arise, and to alert any HCP not familiar with MTX treatment about the once-weekly dosing regimen e.g. on hospital admission, change of care etc.)
  - 3.2. Knowledge of the once-weekly dosing frequency of MTX in the treatment of inflammatory diseases (e.g. rheumatologic/dermatological diseases or Crohn's disease), for his/her indication

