#### 9.2.1 Participant selection

#### 9.2.1.1 Prescriber Selection

Choice of the specialties to include in the survey will be based on the specialties that have been targeted for distribution of the DHPC and educational material (EM) by the relevant national competent authorities in the selected countries, for e.g. specialists including GPs, internists, rheumatologists, dermatologists, gastroenterologists etc. The choice of specialties can be variable between countries. To the extent possible, prescribing patterns will be obtained from IQVIA data assets as supportive evidence to document the choice of specialties. Please refer to Annex 2. List of Healthcare Professionals for a complete list of prescribers who received the DHPC/EMs per country.

In the absence of comprehensive lists of MTX prescribers, the initial sampling frame for the identification of participating prescribers will be based on the list of all prescribers (OneKey, IQVIA, OneKey is an IQVIA managed database with information of health care professionals) in each of the relevant specialties in the targeted country. OneKey databases are constructed and updated through manual and automated means from various sources, including publicly available sources. OneKey is the most comprehensive list of HCPs in the

Template No.: RWI\_TP\_EPI0016 Revision 1 Reference: RWI\_WI\_EPI0005

Protocol/Study No: SC02 EMA/2018/19/PE

Page 28 of 92

world with very high coverage in most countries (33). Also, in EU PAS Register, it can be seen where OneKey database has been used for other post-authorisation safety studies (PASS) such as EUPAS34465 and EUPAS32142.

Since the study objective is to determine the extent of prescriber awareness and knowledge of the risk of inadvertent overdose due to daily instead of weekly use of MTX, only prescribers who have prescribed in indications requiring once-weekly MTX (in the past 3 months) will be selected. As this information is not available in the lists of prescribers, the survey will be preceded by a set of questions to check the eligibility of prescribers. Among these, it will be asked if the prescriber has prescribed in indications requiring once-weekly MTX in the past 3 months. If the answer is no, the survey will not be administered to that prescriber.

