#### 9.4.3 Questionnaire development

Each questionnaire i.e. prescriber, pharmacist and patient questionnaire was developed in English. The questionnaires were designed to be non-directing, clear, to avoid inducement of social desirability and had no self-evident answers. Each questionnaire included questions about screening criteria, demographics, receipt and awareness of MTX EMs, and knowledge about MTX risks. The prescriber and pharmacist questionnaire had additional questions about self-declared behaviour.

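### Once-weekly methotrexate use or prescribing is an entry condition for surveys that then measure knowledge of that frequency, which pushes the dosing-frequency items towards success

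*Protocol*

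**What the plan says.** All three entry criteria in Protocol section 9.2.2 name the regimen.

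- Patients: "Patients who have been treated with a single low dose once a week for indications that require weekly dosing in the past 3 months".
- Prescribers: "Prescribers who have prescribed MTX in a single low dose once a week for indications that require weekly dosing in the past 3 months".
- Pharmacists: "Pharmacists who have dispensed MTX in a single low dose once a week for indications that require weekly dosing in the past 3 months".

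Section 9.2.4 defines the target populations in the same terms. For patients it refers to having used a weekly dose. On timing, the Abstract (Population) says: "The following criteria will be checked at the beginning of the web questionnaire".

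Section 9.2.1.1 describes the prescriber screener a little differently: "it will be asked if the prescriber has prescribed in indications requiring once-weekly MTX in the past 3 months". It adds: "If the answer is no, the survey will not be administered to that prescriber".

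Objective 3.2 in section 8 is, for patients: "Knowledge of the once-weekly dosing frequency of MTX in the treatment of inflammatory diseases". Objective 1.2 asks prescribers for the dosing frequency by indication. Section 9.4.3 says that the questionnaires "had no self-evident answers".

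**The concern.** The risk-minimisation measures exist because methotrexate is sometimes taken daily in place of weekly. A survey of whether they worked has to be able to find people who hold that misconception.

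Two mechanisms work against this.

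1. **Selection (patients).** A patient who takes the drug daily, or believes that is the schedule, cannot truthfully say that they were treated once a week. That patient can be turned away before any knowledge item is asked.
2. **Cueing (patients and prescribers).** A screener that follows the criteria states the frequency first. Section 9.4.1 bars respondents from going back to earlier answers so as to limit information bias, but that gives no protection when the opening page has already supplied the answer.

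Both favour success on the items behind primary objectives 1.2 and 3.2. Section 9.9 does not cover either. Section 9.9.1 treats selection as volunteer bias and presents the three-month weekly criterion as protection against recall bias. Section 9.9.4 concerns only prescribers and pharmacists who have not yet prescribed or dispensed weekly methotrexate. Weighting by country cannot repair the selection, because people who are screened out leave no answers.

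**Working it through.** **The plan's own figure.** Section 9.5.1, with P = 0.5, z = 1.96 and e = 0.08: n = 0.25 × 1.96² / 0.08² = 150.06. The stated 150 reproduces. It describes sampling error only, and the problem here is systematic.

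**Selection, dosing-frequency items.** Let K be the true share who know the weekly schedule and f the share of the others who are screened out. The protocol gives neither, so both are assumptions.

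Observed share = K / [K + (1 − K)(1 − f)]

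| K | f | Calculation | Observed |
|---|---|---|---|
| 70% | 5% | 0.70 / (0.70 + 0.30 × 0.95) | 71.1% |
| 70% | 10% | 0.70 / (0.70 + 0.30 × 0.90) | 72.2% |
| 70% | 25% | 0.70 / (0.70 + 0.30 × 0.75) | 75.7% |
| 70% | 50% | 0.70 / (0.70 + 0.30 × 0.50) | 82.4% |
| 75% | 10% | 0.75 / (0.75 + 0.25 × 0.90) | 76.9% |
| 75% | 25% | 0.75 / (0.75 + 0.25 × 0.75) | 80.0% |

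**Cueing.** If a share c of the uninformed who do enter is put right by the screener wording, the observed share p becomes p + (1 − p)c. With K = 70%, f = 25% and c = 25% (again assumed): 0.757 + 0.243 × 0.25 = 81.8%.

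**Composite verdict.** Annex 5 judges knowledge on a total score, not on dosing frequency.

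- Patients need 20 of 25 points, from Q7 (6), Q8 (4), Q10 (6) and Q11 (9). A patient can get five sub-questions wrong and pass.
- Prescribers need 13 of 16 and can get three wrong.

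Write a and b for the composite pass rates among those who do and do not know the frequency, and m = (1 − K)f for the share screened out. Assume that those screened out would have passed as often as the other uninformed respondents. Then:

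- Shift on a frequency item = K × m / (1 − m).
- Shift on the composite pass rate = K × m × (a − b) / (1 − m).

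The composite shift is the item shift multiplied by (a − b). It is smaller unless everyone who knows the frequency passes and everyone who does not fails. The protocol gives no information on a or b.

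**Prescriber screener against prescriber criterion.** Section 9.2.2 conditions on the schedule that was prescribed. Section 9.2.1.1 asks about prescribing in indications that require weekly dosing, which conditions on indication. A prescriber who mis-schedules the drug in such an indication fails the first and can truthfully pass the second. Both wordings name the weekly frequency.

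**The case against.** The other side has several good points.

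- **Prescribers.** A reader might infer that every prescriber who mis-schedules methotrexate is excluded. The document does not support that, because the section 9.2.1.1 screener turns on indication. For prescribers, f could be near zero. Objective 1.2 is also by indication, and the screener as described gives the frequency without listing the indications to which it applies.
- **Screener text.** The questionnaires are stand-alone documents (Annex 1) and are not shown. The criteria may be checked without being displayed word for word, and no patient screener wording appears in the protocol. Cueing is what follows if the screener tracks the criteria; it has not been observed.
- **Pharmacists.** They share the criterion, but objective 2 has no dosing-frequency element, so this mechanism does not reach that survey.
- **The 80% threshold.** A reader might set the 82.4% or 80.0% above against it and conclude that the study verdict flips. The threshold applies to composite scores, so the figures do not show that.
- **Occasional errors.** A patient prescribed weekly treatment who once took it daily by accident can still enter, and Q18 asks about this. Q18 is outside the assessment of success.
- **Stated limits.** Section 9.9.1 concedes that more aware people may take part. The direction of bias is the same, but the mechanism is different.

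It could also be said that the estimates are valid for the target population as defined. That is true, but section 9.2.4 defines that population by the behaviour under study, so the mismatch with objective 3.2 remains.

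What stands is the patient criterion, the risk of cueing in both surveys, and the silence of section 9.9.

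**Conclusion.** The point holds in limited form. Entry is conditioned on the regimen whose knowledge objectives 1.2 and 3.2 measure. Patients who believe in or practise daily use can be screened out. If the screener follows the criteria, patients and prescribers meet the frequency before the knowledge items, which is at odds with section 9.4.3. Whether erring prescribers are excluded is uncertain, because sections 9.2.1.1 and 9.2.2 differ and must be reconciled. The pharmacist survey is not affected by this mechanism.

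The bias runs towards success on the dosing-frequency items: about 2 points at K = 70% and f = 10%, about 6 at f = 25%, and about 12 at f = 50%, before any cueing. K, f and c are all assumed. The effect on the composite 80% verdict is smaller, on the assumption stated above, and its size cannot be derived from the protocol. The change is worth making because it is simple and the bias cannot be removed once the data are in.

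**What to change.** For prescribers and patients:

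1. In the Abstract and in sections 9.2.1.1, 9.2.2 and 9.2.4, define eligibility and target population as methotrexate prescribed or used in the past 3 months for a listed inflammatory indication, with no frequency named. This also reconciles the two prescriber wordings.
2. Screen out oncology-only use by an indication question. Section 9.3.2.3 already collects the patient's indication.
3. Keep frequency wording out of the screener and, as far as possible, out of the invitation. Section 9.2.4 requires the invitation or first contact to explain background and objectives, so some wording there may be unavoidable.
4. Ask the frequency item first, before the awareness items that mention the weekly reminder (patient Q3 to Q6 in Annex 5.3). This departs from the awareness-first order in section 9.4.1, which needs a matching edit.
5. Report the number screened out, by reason.

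The sample size does not change. The cost is rewording, forward and back translation, and renewed EMA review under section 9.4.4, possibly with ethics review in Poland (Table 5).

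Version 2.0 is dated 21 February 2022, inside the planned collection window of 1 January to 30 April 2022 (section 6). If fieldwork has already started, the minimum is to report screen-out counts and to state the selection and the cueing as a limitation in section 9.9.

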#### 9.2.3 Exclusion Criteria

Participants meeting the following criteria are not eligible for participation:

- Prescribers, pharmacists, or patients who declare having a conflict of interest with the survey (i.e. participants employed by regulatory bodies, pharmaceutical industries)
- Prescribers, pharmacists, or patients who do not provide consent for participating in the survey

# 9.2.4 Study Enrolment

The following groups will be considered as the target population:

- All prescribers within the selected specialties in the selected countries who have prescribed a weekly dose of MTX in the past 3 months
- All pharmacists in the selected countries who have dispensed a weekly dose of MTX in the past 3 months
- All patients in the selected countries who have used a weekly dose of MTX in the past 3 months

The survey will be conducted by IQVIA's Global Primary Intelligence, a division of IQVIA specialised in the conduct of phone and web surveys for more than 20 years. IQVIA's Global Primary Intelligence will create a web-based survey. Prescribers, pharmacists and patients' answers/data will be collected through this web survey. Participants will be randomly contacted, mainly by email, and phone or letter when needed, according to their stratum.

The targeted prescribers will be randomly selected and enrolled on an ongoing basis until the study size is reached (37). Random selection of prescribers and pharmacists is performed to minimise selection bias.

An equal distribution of age, gender and indication for MTX treatment cannot be made throughout recruitment, but a quota can be built into the survey to allow certain numbers for each of these categories. However, this may result in a longer period of recruitment and lower number of respondents. If this is the case, we will remove the quota at some point during the fieldwork, to recruit the pre-defined sample size. It should also be noted that the survey was not designed to provide a representative sample across age categories, gender, or indication for MTX.

